Group A: The Control group received conventional physical therapy (Stretching followed by Strengthening program and traditional gait training) at clinical setting. Stretching muscles were hip flexors, hip adductors, hamstrings and calf and stretching applied for 30 sec with 30 sec rest for 3 -5 times for each muscle group with in pain limit followed by strengthening exercise for weak muscle which includes the strengthening of anti-gravity muscles of lower limb they are: Quadriceps, Gluteus maximus and soleus performed in 3 groups. Each group contain 10 rep for each weak muscle group. Conventional Physical therapy applied 5 days/week for consecutive 20 weeks. They were also guided to perform activities at home but they're unbound to do the designed activities freely.

Group B: The experimental group will receive Lower extremity functional training (LIFT) at home environment and routine physical therapy at clinical setting. LIFT will be provided at home environment for 3 hours/day, 5days/week for 5 months. A log book will be maintained and the goals and strategies will be guided to child's parents. 3 hours' treatment will be performed in intervals at different time of the day. LIFT will help the child in motor learning, skill progression and resistance training to target the strength, proprioception and coordination impairments of the lower extremities. Motor learning will be based on Strength domain (Cycling) and progression from smooth to rough surface. Balance and Coordination domain involves activities such as (ball kicking with alternate legs and Static standing) and progression will be done by increasing accuracy and complexity. Proprioception domain (Vertical jumping, sit to stand and cursing) while applying knee-immobilizers if needed and progression number of repetitions and sets will be increased over time. Skill progression will be used to challenge the LIFT and make it intensive enough to obtain changes in motor skills and function. AFO's will be required during therapy session if needed.

Caregiver will be provided proper guidelines before implementing the treatment at home. 3 training sessions will be given prior to treatment. A log book will also be provided to get the structured record of the treatment. Further videos and mode of tele-rehabilitation will be used for supervision and guidance throughout the study. Therapist will closely monitor the activities by checking daily logs.

Data Analysis Procedure

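### No collection or analysis of harms is specified in either arm, although each LIFT child is scheduled for about 300 hours of caregiver-led home training

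*Combined protocol and SAP*

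**What the plan says.** The Group B description sets the dose: "LIFT will be provided at home environment for 3 hours/day, 5days/week for 5 months". Caregivers deliver it after three training sessions. The content includes cycling that moves on to rough surfaces, ball kicking, vertical jumping and sit-to-stand, with knee immobilisers or ankle-foot orthoses where needed.

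Three monitoring channels are described for this arm:
- **Log book:** "A log book will also be provided to get the structured record of the treatment".
- **Remote contact:** "Further videos and mode of tele-rehabilitation will be used for supervision and guidance throughout the study".
- **Therapist review:** "Therapist will closely monitor the activities by checking daily logs".

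Group B also attends routine physical therapy at the clinic, at a frequency that is not stated.

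For Group A the plan says "Conventional Physical therapy applied 5 days/week for consecutive 20 weeks", at the clinic. On home activity it says "They were also guided to perform activities at home", and leaves these children free in how they do so. No log is described for them.

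The Data Analysis Procedure names four outcomes: GMFM-88, the 6-minute walk, Timed Up and Go and the 30-second chair test. All measure motor capacity or performance. Pain is mentioned once in the whole document, as a limit on Group A stretching.

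**The concern.** Children with spastic diplegia, in a trial aimed at their gait and balance, are to jump and cycle at home under a caregiver for 15 hours a week. Falls and pain are foreseeable. The plan gives no definition of such an event, no field for it, no route for reporting it and no table to hold it.

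Two things are at stake. First, the trial could report benefit from an intensive home programme and be unable to say anything quantitative about its harms. Harm data that were not collected cannot be recovered at the analysis stage. Second, an event that came to light informally would do so through a log or tele-contact in one arm and mainly through clinic attendance in the other. Counts assembled that way could not be compared.

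**Working it through.** **1. What is specified, side by side**

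| Item | LIFT (Group B) | Control (Group A) |
|---|---|---|
| Written record | Log book of treatment, checked by therapist | None described |
| Remote contact | Videos, tele-rehabilitation | None described |
| Clinic contact | Routine therapy, frequency not stated | 5 days/week for 20 weeks |
| Harm definition, field or reporting route | None | None |
| Harm outcome or analysis | None | None |

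The last two rows establish the omission. The first three show that the channels differ between arms.

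**2. The plan's own numbers**

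The Sample Size section gives 35 per group and adds 20% for dropout: 35 × 0.20 = 7, and 35 + 7 = 42, as stated. With a difference of 17.25 − 13.25 = 4.00 and a common SD of √((6.25² + 5.12²)/2) = 5.713, two-sided 5% and 80% power give 33 per group, close to the stated 35. Nothing here depends on that gap. The figures 35 and 42 serve below as the low and high number of children per arm.

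**3. Scheduled LIFT exposure**

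The plan states no total, so it is derived from the dose.
- Taking five months as the 20 weeks stated for Group A: 3 × 5 × 20 = 300 h per child.
- Taking five calendar months: 5 × 52/12 = 21.67 weeks, and 15 × 21.67 = 325 h per child.
- Over the arm at 300 h: 35 × 300 = 10,500 h; 42 × 300 = 12,600 h.

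These are scheduled hours at full adherence; actual hours would be lower.

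**4. What systematic collection would buy**

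If n children are all assessed and none has an event, the one-sided 95% upper limit for the proportion affected is 1 − 0.05^(1/n).
- n = 42: 1 − 0.05^(1/42) = 6.9%.
- n = 35: 1 − 0.05^(1/35) = 8.2%.

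Without systematic collection, the absence of reported events supports no such limit.

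**5. Contact in the control arm**

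5 × 20 = 100 scheduled clinic days per child. The matching figure for LIFT cannot be computed, because its clinic frequency is not given.

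**The case against.** The strongest reply is that LIFT children are far from unobserved. Videos and tele-rehabilitation run throughout, a therapist reads the logs, and the children also attend a clinic. The log's fields are not listed, so it might have room for a fall or a sore knee. All of this stands. It rules out two inferences a reader might draw: that the log is the only monitoring, and that harms would never be noticed. It does not supply a definition, a reporting route or an analysis, so an event that was noticed still has no specified place in the trial's data.

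A reader might also infer that ascertainment would run against LIFT because only that arm has a log. The documents do not support a direction. Control children have about 100 scheduled clinic days, LIFT clinic frequency is unknown, and no capture rates are given. No harm comparison is planned either. What stands is only that the channels differ.

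A reader might see a contradiction in the pain limit attached to Group A stretching: "stretching applied for 30 sec with 30 sec rest for 3 -5 times for each muscle group with in pain limit". It qualifies one technique. Group A strengthening carries no such limit either, so the two arm descriptions do not conflict on this.

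Two practical objections also stand. The Statistical Procedure section says in the past tense that normality was checked and tests were applied, so new prospective fields may come too late. And a daily log for Group A could alter a comparator that leaves home activity unstructured. The fix allows for both.

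**Conclusion.** The omission is real and worth correcting. No definition, collection or analysis of falls, pain, injury or orthosis problems is specified for either arm. LIFT monitoring is described for delivery and guidance, with no counterpart record in control. About 300 scheduled hours per LIFT child (325 on the calendar-month reading) would therefore produce no systematic harm data, and incidental reports could not be compared between arms.

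The exposure totals assume 35 to 42 children at full adherence. The limits of 6.9% and 8.2% assume no events and complete assessment of every child counted. These figures scale the omission; they are not evidence that harm occurred or that the efficacy comparison is biased.

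**What to change.** **If data collection is still open:**
- Add fixed fields to the existing LIFT log: fall; pain and its site; skin or orthosis problem; session shortened and why. The therapist who already checks the log passes any positive entry to the investigator.
- For the between-arm comparison, ask the same short fall, pain and injury questions at the same fixed interval in both arms, at existing clinic contacts. Because LIFT clinic frequency is not stated, choose an interval that both arms' contacts allow. This avoids giving Group A a daily activity log.
- Report the number of children with at least one event by randomised arm, from the common questions only. Describe log-sourced LIFT events separately, since control has no matching source.

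**If data collection is complete:** extract harms by the same method from both arms' clinic records, or state in the report that harms were not systematically collected.

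The cost is a little more paperwork for caregivers and clinic staff, and one descriptive table. No extra visits are needed and the sample size is unchanged. Nothing here proposes a change to treatment content or progression.

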**EFFECTS OF LOWER LIMB INTENSIVE FUNCTIONAL TRAINING ON
GAIT AND BALANCE IN SPASTIC DIPLEGIC CEREBRAL PALSY
CHILDREN**

NCT NO: None

Document Date: January 10,2023

Study Protocol:

Objective:

1. To compare outcomes of lower limb intensive functional training (LIFT) with conventional physical therapy on gait and balance in spastic diplegic cerebral palsy children.
2. To access if changes in motor capacity can further improve their motor performance level.

Study Design:

Randomized Controlled Trial

Study Method:

Settings

Children with Spastic diplegic from Physiotherapy Department of 2 different centers from Lahore.

Duration of Study

Duration of study was 9 months after approval of synopsis.

Sample Size

The calculated sample size using 30-sec chair test as outcome measure is 35 in each group after adding 20% dropout the sample size will be $35+7=42$ in each group.

$$n = \frac{2\sigma^2(z_{1-\alpha/2} + z_{1-\beta})^2}{(\mu_1 - \mu_2)^2}$$

$Z_{1-\alpha/2}$ Level of significance=95%

μ_1 Expected mean change in 30 sec chair rise test in Control group= 17.25

μ_2 Expected mean change in in 30 sec chair rise test in Experimental group= 13.25

δ_1 Expected standard deviation in Control group = 6.25

δ_2 Expected standard deviation in Experimental group = $5.12Z_{1-\beta}$

power of the study= 80%

n Expected sample size in a group= 35

After adding 20% drop out $35+7=42$ in each group.

Sampling Technique

Non-probability Purposive sampling technique was used.

Statistical Procedure:

SPSS version 21 was used for data entry and analysis. Quantitative variables presented with mean \pm SD and qualitative variables presented with frequency and percentage. Normality of the data was assessed with Shapiro-Wilk test. The data not fulfilled the assumption of normality. So, non-parametric test Friedman and Mann Whitney U test were applied. The p-value <0.05 was considered statistically significant

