Data will be analyzed using IBM SPSS version 21. The quantitative variables like age will be presented in the form of mean \pm SD and qualitative variables like gender will be presented in the form of frequency and percentage. After checking normality of data if parametric tests will be required the independent sample t-test will be used to determine mean difference of GMFM-88 for motor capacity and 6-min walk test, Timed Up and Go test and 30 sec chair raise test for motor performance. Further, mixed model will be used to compare the outcome variables at follow-ups on the other side if data will not be normally distributed then Friedman test will be used. P-value ≤ 0.05 will be considered as significant.

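### The only test that the Data Analysis Procedure names for non-normal data is Friedman, which cannot compare LIFT with control; one baseline-adjusted between-arm test should be named

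*Combined protocol and SAP*

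**What the plan says.** Objective 1 in the combined protocol and SAP is a comparison between arms: "To compare outcomes of lower limb intensive functional training (LIFT) with conventional physical therapy on gait and balance".

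Two sections describe the analysis.

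- **Data Analysis Procedure** (future tense). If parametric tests are suitable, "the independent sample t-test will be used to determine mean difference of GMFM-88 for motor capacity and 6-min walk test", with the Timed Up and Go and 30-second chair tests also listed. A "mixed model will be used to compare the outcome variables at follow-ups". In the same sentence comes the rule for the other case: "if data will not be normally distributed then Friedman test will be used". No other non-parametric test is named.
- **Statistical Procedure** (past tense). "The data not fulfilled the assumption of normality". "So, non-parametric test Friedman and Mann Whitney U test were applied".

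Neither section says at which visit the arms are compared, or whether the score is the last value or the change from baseline. The documents list no assessment visits. The Sample Size section uses the label "Expected mean change in 30 sec chair rise test in Control group" but does not tie it to any analysis.

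**The concern.** The non-normal branch is the one that applied, because the Statistical Procedure says so. In that branch the Data Analysis Procedure offers a test of change over time and nothing that compares the arms. Followed as written, it leaves Objective 1 unanswered.

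The Statistical Procedure adds Mann-Whitney U, which can compare two independent arms. That narrows the problem but does not remove it. The two sections name different tests for the same situation, and the test that bears on the treatment question has no stated visit or scale. Where those are open, they can be settled after the results are known. Separately, a significant Friedman result could be misread as evidence for LIFT.

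**Working it through.** **1. Test against question.**

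| | Data Analysis Procedure | Statistical Procedure | Can it compare the arms? |
|---|---|---|---|
| Independent-samples t-test | yes, if normal | not named | yes |
| Mixed model | yes, if normal | not named | depends on its terms, which are not listed |
| Friedman | yes, if not normal | yes | no |
| Mann-Whitney U | not named | yes | yes |

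**2. Why Friedman cannot do it.** The statistic is built from the ranks of each child's own visits. Moving a child from one arm to the other leaves those ranks unchanged, so a Friedman test on all children gives the same p-value however the arm labels are assigned. Run separately in each arm, it gives two within-arm p-values, and contrasting them is not a test of the difference. If both arms follow the same course and each Friedman test rejects with probability p, the chance of significance in LIFT only is p(1 − p). At p = 0.5 this is 0.25, with no treatment difference at all.

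**3. The plan's sample size, which sets the arm size used below.** Inputs from the Sample Size section: means 17.25 and 13.25 (difference 4), SDs 6.25 and 5.12, two-sided 5%, power 80%.

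- Pooled SD = √((6.25² + 5.12²)/2) = √((39.06 + 26.21)/2) = 5.713
- n = 2 × 5.713² × (1.960 + 0.842)² / 4² = 32.02, so 33 per arm; a t-based calculation gives 33.01, so 34

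The stated 35 is close to this. The point does not depend on it.

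**4. What an open choice of scale could do.** Assumptions: no true difference, 35 per arm, equal SDs, baseline-to-last-visit correlation r of 0.3, 0.6 or 0.8, and normal or skewed scores (standardised lognormal, sigma 0.7). There were 20,000 simulated trials per cell, so the simulation standard error near 5% is √(0.05 × 0.95/20,000) = 0.15 percentage points. These error rates do not depend on the SD.

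| Type I error, % (r = 0.3 / 0.6 / 0.8) | Normal | Skewed |
|---|---|---|
| Mann-Whitney, last score | 4.9 / 5.2 / 4.8 | 5.1 / 5.0 / 5.0 |
| Mann-Whitney, change | 5.0 / 4.9 / 5.1 | 4.6 / 4.6 / 5.0 |
| Better of these two | 8.8 / 9.3 / 9.5 | 8.7 / 9.0 / 9.5 |
| t-test, better of last score and change | 9.1 / 9.2 / 9.6 | 8.4 / 8.4 / 8.9 |
| Rank ANCOVA, specified once | 5.0 / 5.1 / 4.9 | 5.2 / 4.8 / 5.4 |

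The size is plausible on simple grounds. Two 5% tests cannot together exceed 10%, and two independent ones give 1 − 0.95² = 9.75%. With equal SDs, the correlation between last score and change is √((1 − r)/2), which is 0.59, 0.45 and 0.32 for the three values of r. The two tests therefore overlap only in part.

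**5. Whether the proposed test gives anything up.** Rank ANCOVA here means regressing last-visit ranks on baseline ranks and comparing the residuals by arm. In simulation its power was at least about that of Mann-Whitney on either scale in every cell, within simulation error. With skewed scores, a 4-point difference and 10,000 trials per cell, and with 5.71 taken as the SD of either the raw score or the change, the power was:

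- Mann-Whitney on last score: 85.2% to 99.7%
- Mann-Whitney on change: 86.7% to 99.9%
- Rank ANCOVA: 98.9% to 100%

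These figures rest on the assumed lognormal shape and are illustrative.

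**The case against.** The strongest reply is that the treatment comparison exists. The Data Analysis Procedure is a conditional plan. The Statistical Procedure reports what was done, and it lists Mann-Whitney U, which in a two-arm trial is almost certainly the test between arms. The sentence that introduces Friedman also introduces the mixed model for follow-ups, so Friedman may have been meant only as the counterpart of that model, with Mann-Whitney U as the counterpart of the t-test.

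Most of this stands. A reader might infer from the Data Analysis Procedure alone that no between-arm test was planned or run; the documents taken together do not support that. But if Friedman replaces only the mixed model, the Data Analysis Procedure names no non-parametric counterpart to the t-test, and the conflict between sections remains.

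Four other inferences go too far.

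- *The false-positive rate was inflated.* The 8% to 10% arises only if the better of two results is picked. Nothing shows that it was.
- *Friedman was run on both arms together.* The documents do not say whether the arms were pooled or how many visits there were.
- *The mixed model has the same defect.* Its terms are not given, so nothing can be said either way.
- *The sample size label settles the scale.* It points to change for the chair test, but it is a planning input for one outcome and does not bind the analysis.

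It is also fair to say that a Mann-Whitney test with a stated visit and scale holds its level, and that rank ANCOVA appears nowhere in the documents. The case for rank ANCOVA is that it uses baseline, removes the choice between last score and change, and costs little.

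**Conclusion.** The point holds in a limited form and should be fixed. The only rule that the Data Analysis Procedure states for non-normal data is a test that cannot answer Objective 1, and it disagrees with the Statistical Procedure about which tests apply. That conclusion rests on the text and on the construction of the Friedman test, not on simulation.

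The unstated visit and scale would be missing detail on their own. They matter here because the between-arm test appears only as a name. The possible cost is a rise in type I error from about 5% to about 8% to 10% on one outcome. This is conditional on choosing the scale after seeing results, and on the assumptions of 35 per arm, correlation 0.3 to 0.8, and normal or skewed scores. The t-test lacks a visit and scale too, but that branch was not the one used.

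**What to change.** 1. In the Data Analysis Procedure, name one between-arm test for Objective 1 when data are not normal: a rank ANCOVA of the end-of-treatment score adjusted for baseline. State which assessment counts as end of treatment.
2. Report the Mann-Whitney U already applied as a supporting analysis, giving the visit and scale actually used.
3. Keep Friedman as within-arm description, with a sentence saying that it cannot support a conclusion about treatment.
4. Make the Data Analysis Procedure and the Statistical Procedure name the same tests.
5. Label any re-analysis as post hoc.

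The cost is wording and a short re-run on data already collected: ranking, one regression and one comparison of residuals between arms for each outcome. The drawback is that this cannot restore prespecification, because the tests have already been applied. Rank ANCOVA would itself be chosen after data collection, so it should be shown alongside the Mann-Whitney result whatever the two show.

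### Four outcomes share one 0.05 threshold with no stated primary, correction, testing order or success rule, so the error rate of the trial's conclusion is undefined; it is about 9-19% if any one of the four can carry the claim

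*Combined protocol and SAP*

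**What the plan says.** The Data Analysis Procedure sets out the comparison between groups under its parametric branch: an "independent sample t-test will be used to determine mean difference of GMFM-88 for motor capacity", and likewise for the "6-min walk test, Timed Up and Go test and 30 sec chair raise test for motor performance". A "mixed model will be used to compare the outcome variables at follow-ups", with Friedman as the alternative when data are not normal. One threshold covers everything: "P-value ≤ 0.05 will be considered as significant".

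The Statistical Procedure section reports that normality was not met and that Friedman and Mann-Whitney U were used, again at 0.05. It does not list the outcomes tested.

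The Sample Size section uses a single outcome: "The calculated sample size using 30-sec chair test as outcome measure". It does not call that outcome primary. Objective 1 compares LIFT "with conventional physical therapy on gait and balance in spastic diplegic cerebral palsy children", and the title likewise speaks of gait and balance.

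None of these sections names a primary outcome, a multiplicity correction, an order of testing or a rule for declaring LIFT successful.

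**The concern.** A 0.05 threshold controls the error of one test. It controls the error of a trial's conclusion only if the plan says which test, or which combination of tests, carries that conclusion. Here four outcomes stand side by side and nothing says how many must be significant, or which.

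Under the rule as written, one significant result out of four could be presented as the trial's finding when it is due to chance. Naming a primary after the results are known does not repair this. If the best of the four is chosen, the error is the same as for four unadjusted tests.

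**Working it through.** **The plan's own figure.** Inputs from the Sample Size section: means 17.25 and 13.25 (difference 4), SDs 6.25 and 5.12, two-sided 5%, power 80%.
- Average variance: (6.25² + 5.12²)/2 = 32.64, so SD = 5.713.
- n = 2 × 32.64 × (1.960 + 0.842)² / 4² = 32.0; with the small-sample t correction, 33 per group. The plan states 35, which is close.
- 35 × 1.2 = 42, as stated.

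This calculation covers one outcome tested once at 5%.

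**Error across several outcomes.** Assume that no outcome truly differs, that there is one between-group test per outcome at two-sided 0.05, and that significance on any one is enough for the claim. With independent tests:
- Four tests, either direction: 1 − 0.95⁴ = 0.1855.
- Four tests, in favour of LIFT: 1 − 0.975⁴ = 0.0963.
- Three motor performance tests, either direction: 1 − 0.95³ = 0.1426.

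The documents give no correlations between outcomes, so a range of common pairwise correlations ρ is assumed. For normal test statistics sharing one common factor, the error is 1 − ∫ φ(u) [Φ((1.96 − √ρ·u)/√(1−ρ)) − Φ((−1.96 − √ρ·u)/√(1−ρ))]^k du. The second Φ term is dropped for the one-directional figure.

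| Assumed ρ | Four tests, either direction | Four tests, favouring LIFT | Three performance tests, either direction |
|---|---|---|---|
| 0 | 18.5% | 9.6% | 14.3% |
| 0.5 | 15.6% | 7.8% | 12.5% |
| 0.7 | 13.0% | 6.5% | 10.9% |
| 0.9 | 9.4% | 4.7% | 8.4% |
| One test | 5% | 2.5% | 5% |

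Simulated Mann-Whitney tests with 35 per group agree for four outcomes, either direction: 18.1%, 15.5%, 13.5% and 9.7%.

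**The remedies in the same simulation.** Holm across four gives 4.7%, 4.1%, 3.6% and 2.6%. A chair-test gate fixed beforehand gives 4.8-5.0%. Choosing the best of four afterwards gives the unadjusted rates.

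**Chair-test power.** Mann-Whitney simulation on the plan's means and SDs, with normal data:

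| Evaluable per group | At 0.05 | At 0.0125 (= 0.05/4) |
|---|---|---|
| 35 | about 80% | about 61% |
| 42 | about 87% | about 71% |
| 50 | not needed here | about 80% |

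The row for 42 requires that nobody drops out. A 20% loss leaves 42 × 0.8 = 33.6, about 34 per group, with power of about 79% at 0.05.

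**The case against.** The strongest reply is that the chair test is the implicit primary. It is the only outcome used for sizing, at 5% and 80% power. On that reading the error on the primary claim is 5% and the 9-19% does not apply. This is plausible, but the documents never say it. The analysis section lists the chair test last of four with no special standing, and the title and objective 1 concern gait and balance.

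Second, the family of four is not explicit for the analysis actually used. The only sentence linking all four to a between-group test is conditional on parametric tests, and normality failed. The non-normal branch names only Friedman, a within-subject test that cannot by itself compare the groups. Mann-Whitney on the same four outcomes is the natural reading, but it remains an inference. Objective 2 also separates motor capacity from motor performance, which is why the three-test figures are shown.

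Third, the plan does not state that any one significant result will count as success. It merely fails to exclude this. The 18.5% end also needs zero correlation among four motor tests in the same children.

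A reader might infer from the past tense of the Statistical Procedure that a primary was left open until the results were known. The documents do not support that. Tenses are mixed throughout, the Data Analysis Procedure is in the future tense, and the approved synopsis that is mentioned is not part of what was supplied. The documents are silent on timing.

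**Conclusion.** The point stands as an omission with a conditional size. The plan defines neither a primary outcome nor an error family. The error on the trial's conclusion therefore depends on a reading that the documents do not settle:
- chair test as sole primary: 5%;
- any one of the three performance tests: about 8-14%;
- any one of all four: about 9-19%, or about 5-10% in favour of LIFT against 2.5%.

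The last two ranges assume no true difference on any outcome, one between-group test per outcome, and correlations from 0.9 down to 0. It would be too strong to say that the trial has a 9-19% false-positive rate, because that requires an any-one-of-four claim that the plan permits but does not make. Separate between-group tests at several follow-ups would raise the figures, but the number of visits is not given. The sponsor should correct this; the omission is clear, while its size is uncertain.

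**What to change.** State the primary outcome and the error family.

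- **If it can be documented that the chair test was the intended primary before outcome data were seen:** declare its between-group difference the single primary, at two-sided 0.05, with one named test and one named time point. Test the other three outcomes with Holm at 0.05 only if it is significant.
- **Otherwise:** apply Holm at 0.05 across the four between-group tests.

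In both cases keep the planned follow-up analysis (mixed model or Friedman) and state that it lies outside this confirmatory family.

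Also reconcile the sizing inputs. The Sample Size section gives "Expected mean change in 30 sec chair rise test in Control group= 17.25" and "30 sec chair rise test in Experimental group= 13.25", a larger expected change in control than under LIFT. The two-sided sample size does not depend on the sign, but the expected direction of benefit should be clear before the chair test carries the conclusion.

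**Cost.** No new data are needed. With the gate, chair-test power is unchanged (about 80% with 35 evaluable per group; 87% with 42 only if nobody drops out), but no formal claim on the other three outcomes is possible if the chair test fails. With Holm across four, chair-test power at the strictest step is about 61% with 35 and 71% with 42. That is a worst case, because the threshold loosens if other outcomes are rejected first. Reaching 80% at that step would take about 50 evaluable per group; report the reduced power rather than enrol more. All power figures assume normal data, which the Statistical Procedure says did not hold, so true power may differ.
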